8.1 PRETREATMENT EVALUATION

Prior to initiating treatment:

- Prior biopsy with pathologic confirmation of MCL.
- Archival block 10-15 x 10 micron unstained slides and 1 H&E will be requested. A minimum of 40 micron material is requested.
- If archival tissue is not available, patients will be asked to provide informed consent for an optional repeat biopsy.

Within 4 weeks prior to initiating treatment:

- Medical history and demographics
- Complete history and physical exam (including weight, pulse, blood pressure, temperature, ECOG performance status)
- Medication review
- Hepatitis B surface antigen and Hepatitis B core antibody (HBV DNA PCR is only required if HBsAg is positive)
- Hepatitis C antibody
- HIV testing
- Cytomegalovirus PCR testing
- ECG
- Echocardiogram or MUGA to evaluate cardiac function
- PET scan
- CT chest/abdomen/pelvis and neck CT if clinically indicated (MRI will be used for those who are unable to undergo CT scans).

Within 1 week prior to initiating treatment:

- Blood work: CBC with differential, PT/INR, electrolytes (Na, K, Cl, CO2), BUN, Cr, total bilirubin, total protein, albumin, AST, ALT, alkaline phosphatase, uric acid, LDH, magnesium, phosphorus, lipid panel, thyroid function tests, hemoglobin A1c, fructosamine, amylase, lipase, urinalysis, GFR
- Serum beta-HCG (for WOCBP only) to assess for pregnancy

[figure not shown]

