9.8. Management of Toxicities or Procedures

Reproductive Toxicity

Copanlisib may cause embryo-fetal harm. Female patients of childbearing potential are advised to use highly effective contraception (contraception with a failure rate <1% per year) during and up to 1 month after treatment with copanlisib. Advise male patients with female partners of childbearing potential to use highly effective contraception in addition to a barrier method of contraception during and up to 1 month after treatment with copanlisib.

Based on findings in animals, ibrutinib can cause fetal harm when administered to a pregnant woman. Administration of ibrutinib to pregnant rats and rabbits during the period of organogenesis caused embryofetal toxicity including malformations at exposures that were 2-20 times higher than those reported in patients with hematologic malignancies. Advise women to avoid becoming pregnant while taking ibrutinib and for 1 month after cessation of therapy. If this drug is used during pregnancy or if the patient becomes pregnant while taking this drug, the patient should be apprised of the potential hazard to a fetus.

Women of child-bearing potential who are sexually active must use highly effective contraception during the study and for 1 month after the last dose of ibrutinib or copanlisib. Men who are sexually active must use highly effective contraception during the study and for 1 month after the last dose of ibrutinib or copanlisib. Subjects should promptly notify the investigator if they, or their partner, become pregnant during this period. If a female subject becomes pregnant during the treatment period, she must discontinue ibrutinib and copanlisib immediately. Pregnancy in a female subject or a male subject's partner must be reported in the same manner as a SAE. Women are considered post-menopausal and not of child-bearing potential if they have had 12 months of natural (spontaneous) amenorrhea with an appropriate clinical profile (e.g. age appropriate, history of vasomotor symptoms) or have had surgical bilateral oophorectomy (with or without hysterectomy) at least six weeks ago. For women with therapy-induced amenorrhea, oophorectomy or serial measurements of FSH and/or estradiol are needed to ensure postmenopausal status.

Guidelines for Ibrutinib and Copanlisib Management with Surgeries or Procedures

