10.4. Correlative studies

Patients consented on this trial will have tumor samples analyzed for genomic alterations via next generation targeted sequencing. Optional post treatment biopsy will be obtained to compare the differences in genomic alterations prior to treatment and post treatment. In addition, circulating tumor DNA and circulating tumor RNA samples will be collected throughout treatment to serially assess the genomic profile of treated patients.

Gene sequencing will be performed in the CLIA certified Molecular Diagnostics Service laboratory, a division of the MSKCC Pathology Department, using IMPACT-Heme (Integrated Mutation Profiling for Actionable Cancer Targets Hematology Panel) with paired tumor and normal tissue samples, or a custom panel of genes depending on baseline IMPACT-Heme results. IMPACT provides full exon coverage of 410 cancer related genes including CARD11, MYD88, PIK3CA, BTK, and can be used to detect base substitutions, small indels, copy number alterations and select gene re-arrangements. In some cases, the Molecular Diagnostic Service will utilize an additional assay, such as Sanger Sequencing, B cell clonality, or fluorescence in situ hybridization (FISH), to confirm specific results from these multiplexed assays. We will assess for the following:

- 1) Determine variations on circulating tumor RNA throughout treatment
- 2) Correlate spectrum of genomic mutations in tumor tissue versus circulating tumor DNA
- 3) Assess tumor variant allele frequency in circulating tumor DNA
- 4) Correlate circulating tumor DNA to radiographic response

Table 10-1. Schedule of Evaluation

Timepoint	Screening	C1D1	C1D8	C1D15	CxD1	CxD8	CxD15	EOT	30 day FU after last dose ^H
Window	-28	-7		+/- 3 days	+/- 3 days	+/-3 days	+/-3 days	+/- 7 days	+/- 7 days
Treatment									
Copanlisib		X	X	X	X ^A	X ^A	X ^A		
Ibrutinib					Daily				
Evaluation									
Obtain Informed Consent	X								
Demography	X								
Inclusion/Exclusion criteria	X								
Medical/Diagnosis/Treatment history	X								
Prior/Concomitant medications	X		X	X	X				X ^K
Physical Examination	X		X	X	X			X	X
ECOG and Vitals (Weight, Blood pressure, Pulse, Resp, Temp)	X		X	X	X			X	
Hematology: CBC with Diff		X	X	X	X	X		X	
Chemistry(BMP, TBili, AST, ALT, TP, Alb, AP, UA, LDH, amylase, lipase, GFR, Mag, Phos)		X	X Fasting	X	X	X	X	X	
Lipid panel		X				Day 1 Cycle 3, 5, 7, 10, 13, 17, 21, 25, 29, 33			X
Urinalysis, Urine protein						As clinically indicated			X

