T3, T4, TSH		X				As clinically indicated			X
Fructosamine		X			X	X			X
Hemoglobin A1c		X				X			X
Coagulation (PT/PTT)		X							X
B cell Clonality by NGS			X			Day 1 Cycle 3, 5, 7, 10, 13, 17, 21, 25, 29, 33			X
Hepatitis B/C ^B	X					Hepatotoxicity testing/procedures as clinically indicated ^C			
HIV	X								
Cytomegalovirus PCR	X					X			X
Serum/Urine beta-HCG for women of childbearing age		X							
Post Infusion Glucose Evaluation ^D			X ^D Fasting	X ^D	X ^D	X ^D	X ^D		
Post Infusion Blood Pressure ^E			X ^E	X ^E	X ^E	X ^E	X ^E		
Radiographic assessment ^F	X					Before Day 1 Cycle 3, 5, 7 (first 6 months), 10, 13, (1 year), 17, 21, 25, 31 (year 2-3)		X (if not within 4 weeks)	
ECHO or MUGA	X							X	
ECG	X							X	

PCP pneumonia prophylaxis			Continuous (unless clinically contraindicated)				
Pill Diary			X		X		X
Tumor biopsy(archived/fresh biopsy) ^G	X ^G				Optional ^G		
Research Blood Tests: ctDNA, ctRNA		X	X	X	Cycle 2: D1, D8, D15 Cycle 3-7: D1	X	
Research Blood Tests: Pharmacokinetics ^J				X			

A: Copanlisib Dosing: If copanlisib is held based on achievement of a complete response, patient visits will be every 2 cycles during C1-C6, every 3 cycles during C7-C12, every 4 cycles during C13-36.
B: Hepatitis Evaluation: HbsAg, HBcAb, anti-HCV Ab, Hep B/C PCR if positive
C: Additional viral hepatitis workup as clinically warranted: HAAb, HBsAg, HBsAb, HBcAb, HCV RNA or HDV RNA (where needed), H EAb, CMVAb, EBcAb, CMV IgM Ab, EBV IgM Ab, HSV, AP, CPK, LDH, Carriers of hepatitis B should be closely monitored for clinical and laboratory signs of active HBV infection, signs of hepatitis during and for several months following ibrutinib/copanlisib treatment. Carriers of hepatitis B (positive HBsAg and/or HBcAg but negative HBV-DNA is required to be on prophylactic antiviral therapy. If viral load becomes positive, patients should be withdrawn from study. Hep C carriers (anti-HCV Ab positive, negative HCV-RNA PCR must be tested monthly for HCV reactivation. If HCV-RNA PCR becomes positive, patients should be withdrawn from study.
D: Post Infusion Glucose Evaluation: C1D1 – fasting glucose prior to copanlisib (0h), 60 min (end of infusion) and 2 hours; all subsequent doses – non-fasting glucose prior to copanlisib (0h), post infusion.

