13.0 CRITERIA FOR REMOVAL FROM STUDY

Patients may voluntarily withdraw from the study or be removed from the study at the discretion of the investigator at any time. Patients may be withdrawn from the study if any of the following occur:

- Disease progression. However, if progression develops after CR while patient is on ibrutinib alone, patients could restart treatment upon radiographic and pathologic expression of disease.
- Ineligibility (at the pretreatment evaluation) of the patient as defined in the inclusion/ exclusion criteria
- Treatment will be discontinued at the request of the patient, refusal of therapy, non-compliance, or upon the development of an intercurrent significant medical illness.
- Significant protocol violation
- Unacceptable toxicity
 - Grade 4 arterial hypertension
 - Grade 4 dermatologic toxicity
 - Non-infectious pneumonitis
 - Drug induced clinically relevant pancreatitis
 - Grade ≥ 3 hypersensitivity reaction
- Decision by the investigator that termination is in the patient's best medical interest.
- Loss to follow-up

- Development of active HBV or HCV infection, hepatitis, or HIV infection
- Pregnancy or a positive pregnancy test
- Death of the patient

In addition to the general study treatment withdrawal criteria, the following study specific criteria will also require premature study treatment discontinuation:

- Use of prohibited medication
- Start of any other anti-neoplastic therapy

If a study treatment withdrawal occurs, or if the patient fails to return for visits, the investigator must determine the primary reason for a patient's premature withdrawal from study treatment and record this information on the End of Treatment CRF page.

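### Beta-HCG is scheduled once before treatment and not again in up to 36 cycles, although Section 9.8 requires both drugs to stop at once in pregnancy

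*Combined protocol and SAP*

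**What the plan says.** **Risk and stop rule.** The reproductive toxicity text in Section 9.8 warns of fetal harm from each drug. It requires highly effective contraception on study and for 1 month after the last dose, and it sets a mandatory rule: "If a female subject becomes pregnant during the treatment period, she must discontinue ibrutinib and copanlisib immediately". The detection route it gives is self-report: "Subjects should promptly notify the investigator if they, or their partner, become pregnant during this period". Section 13 also lists "Pregnancy or a positive pregnancy test", in a list whose opening words say patients may, not must, be withdrawn.

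**Testing.** Among the assessments due within 1 week before treatment, Section 8.1 lists "Serum beta-HCG (for WOCBP only) to assess for pregnancy". In Table 10-1 the row "Serum/Urine beta-HCG for women of childbearing age" carries one X, in the pre-treatment column. The copanlisib restart criteria in Section 9.9 do not ask for a test.

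**Exposure and visits.** Treatment may run for 36 cycles of 28 days, capped at 36 months. Under Section 4.3, ibrutinib continues daily when copanlisib is held after a complete response. Section 10.2 then spaces visits every 2, 3 or 4 cycles, depending on the cycle reached.

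**The concern.** The Section 9.8 rule can act only once a pregnancy is known, and no scheduled test would make it known. Contraception works before conception. Notification, SAE reporting (Section 17.3) and 24-hour reporting to the copanlisib manufacturer work after recognition.

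The protocol itself gives reasons why self-report may be late in these patients:

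- Everyone has had at least one prior line of therapy (Section 6.2). Section 9.8 recognises therapy-induced amenorrhea and does not accept it alone as proof of postmenopausal status. For such a woman a missed period is not a signal.
- Nausea and fatigue are listed as likely (above 20%) effects of both drugs (Sections 11.5 and 11.7), so early symptoms of pregnancy could be put down to treatment.
- The animal malformations cited for ibrutinib followed dosing during organogenesis, so a late stop may come after the period that matters.

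At stake is continued fetal exposure. No trial estimate is at stake.

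**Working it through.** The plan gives no figure to reproduce. The check is a count of scheduled tests followed by simple arithmetic.

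**1. Scheduled tests.** Section 8.1 and Table 10-1 agree on 1 before treatment. I found 0 on treatment, 0 before a copanlisib restart, 0 at end of treatment and 0 at the 30-day follow-up. Lost table marks are an unlikely explanation. The coagulation row keeps a baseline and an end-of-treatment mark. The row "Urinalysis, Urine protein" keeps an as-needed entry and a later mark. The lipid row keeps "Day 1 Cycle 3, 5, 7, 10, 13, 17, 21, 25, 29, 33". The beta-HCG row has none of these, and its single mark matches the Section 8.1 text.

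**2. Longest treatment with no scheduled test.** 36 x 28 = 1,008 days, and 1,008 / 365.25 = 2.76 years.

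**3. Visit spacing with copanlisib held (Section 10.2).**
- C1-C6: 2 x 28 = 56 days
- C7-C12: 3 x 28 = 84 days
- C13-C36: 4 x 28 = 112 days

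These are upper figures. Section 9.8 also calls for CMV PCR every cycle, and Section 11.6 for monthly blood counts. If those are done, contact is more frequent, but neither is a pregnancy test.

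**4. Expected pregnancies.** Women x years on treatment x yearly failure rate. The number of women is not in the documents; I assume 0 to 2 of the maximum 45 treated patients (Section 14.2). I take the failure rate as 0.01 per year, because Section 9.8 requires below 1%; this presumes adherence.
- 13.9 months on treatment (the ibrutinib PFS in Section 3.0, as a rough duration): 2 x (13.9/12) x 0.01 = 0.023
- 36 months (the cap): 2 x (36/12) x 0.01 = 0.060
- No such women: 0

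**5. Assays under the fix.** Day 1 of C2 to C36 is 35 tests, and 35 + 1 at end of treatment = 36 per woman. For 2 women, 2 x 36 = 72; for none, 0. A restart that does not fall on a Day 1 draw adds one. Time with copanlisib held reduces the count.

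**6. Longest interval between scheduled tests after the fix.** 28 days while copanlisib is given. Up to 112 days while it is held, or 28 if the per-cycle CMV draw is used.

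**The case against.** No section sets a testing interval that the plan breaches. There is a baseline test, mandatory contraception, a strict definition of who is not of childbearing potential, prompt notification, immediate discontinuation and expedited reporting. Scheduled contacts can also reveal a pregnancy or prompt a test: physical examination at Day 1 visits, end of treatment and follow-up; adverse-event questioning at each visit; and PET and CT of chest, abdomen and pelvis before C3, 5, 7, 10, 13, 17, 21, 25 and 31. The expected number of events is close to zero, and the ibrutinib animal findings were at 2 to 20 times patient exposure.

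Much of this stands. A reader might infer that nothing in the plan could bring an unrecognised pregnancy to light; the examinations, questioning and imaging show otherwise. What they do not do is test for pregnancy, and they would tend to find it late. A reader might also take Section 13 as a second mandatory stop rule. Its wording is permissive, so only Section 9.8 compels discontinuation, and that rule applies however the pregnancy is found. Low probability limits the weight of the point, but it does not remove the gap between a mandatory stop and the absence of any scheduled on-treatment test.

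**Conclusion.** The point holds as a low-probability patient-safety improvement that should be made: one pre-treatment beta-HCG, then no scheduled test for up to 1,008 days on two drugs with stated embryo-fetal risk. Expected pregnancies are 0 to about 0.06. That range rests on 0 to 2 women of childbearing potential, 1% yearly contraceptive failure and at most 36 months of treatment. The first is an assumption without support in the documents, and the second presumes adherence.

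Two further inferences are not supported. The first is that the gap bears on the trial's conclusions; error rates, power and the primary analysis do not depend on it. The second is that a woman with a positive baseline test could simply be enrolled because Section 6.3 does not name pregnancy. Section 13 and the investigator-opinion exclusion in Section 6.3 cover that case indirectly, so this is only a missing cross-reference.

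**What to change.** In the beta-HCG row of Table 10-1, for women of childbearing potential only, add a test:

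- on the Day 1 blood draw of every cycle while copanlisib is being given;
- at every scheduled visit while copanlisib is held and ibrutinib continues (every 2, 3 or 4 cycles under Section 10.2), or every cycle if the CMV PCR draw in Section 9.8 is done;
- before any copanlisib restart, with a matching line in Section 9.9;
- at end of treatment.

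Tying the test to the lipid time points instead would be weaker. Those points are themselves 56, 84 and then 112 days apart, even for women still receiving weekly copanlisib, and Section 9.8 gives a different lipid schedule (even cycles).

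The cost is one table row, one line in Section 9.9 and the assays counted above. While copanlisib is given, the draws already exist. While it is held, testing every cycle would rely on the CMV draw or need extra visits; without either, an interval of up to 112 days remains, and the sponsor should accept that knowingly. Optionally, name pregnancy or a positive baseline beta-HCG in Section 6.3.

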- Patient has a concurrent active malignancy. Malignancies treated with a curative intent with an expected life expectancy \geq 5 years or a non-competing life expectancy risk are eligible (i.e. adequately treated basal or squamous cell carcinoma, non-melanomatous skin cancer, early stage breast cancer, treated prostate cancer or any other cancer from which the patient has been disease free for \geq 3 years).
- Patient with known history of human immunodeficiency virus (HIV), or any uncontrolled active systemic infection.
- Patient has CMV viremia (peripheral blood CMV PCR positive), acute viral hepatitis (typically defined by elevated AST/ALT), or a history of chronic or active HBV or HCV infection. HBV infection is defined as having HBsAg and/or HBcAb positive test with concurrent detectable HBV DNA levels. HCV infection is defined as detectable HCV RNA levels.
- Patient requires treatment with a strong or moderate cytochrome P450 (CYP) 3A4 inhibitors, and inducers, and the treatment cannot be discontinued or switched to a different medication prior to starting study drug. Moderate and strong CYP modulators (inducers and inhibitors) should have a washout period of at least 5-6 half-lives before initiating ibrutinib or copanlisib.
- Patients with known bleeding diathesis (e.g. von Willebrand 's disease) or hemophilia
- Patient is currently receiving warfarin or other Vitamin K antagonist. Therapy with heparin, low molecular weight heparin (LMWH), or fondaparinux is allowed. Refer to Section 9.5 for Concomitant medication
- Patients with Child Pugh Class B or C hepatic cirrhosis
- Patients with any life threatening illness, medical condition or organ system dysfunction that in the opinion of the investigator could compromise the subject's safety, interfere with absorption of metabolism of study drugs or put the study outcomes at undue risk.

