Ibrutinib will be administered once daily continuously until disease progression, intolerance, or completion of 36 cycles, not exceeding 36 cycles since start of therapy whichever comes first. Patients will be instructed to take 420 mg or 560 mg depending on the treating cohort.

Ibrutinib should be administered at about the same time each day orally with 8 ounces or approximately 240 mL of water. The drug should be swallowed intact and subjects should not attempt to crush dissolve the tablets in water. If a dose is missed, the dose may be taken as soon as possible on the same day with a return to the normal schedule the following day. Extra tablets of ibrutinib should not be taken to make up for the missed dose. If a patient vomits the dose, the dose should not be retaken. On days when patients are receiving copanlisib and ibrutinib, patients should take their dose of ibrutinib in clinic just prior to the copanlisib infusion.

9.2. Definitions of dose limiting toxicity, maximum tolerated dose, and recommended phase II dose

A dose limiting toxicity (DLT) is defined as any of the following adverse events occurring within cycle 1 (28 days). A maximum tolerated dose (MTD) is defined as the highest dose studied for which the incidence of DLT is less than 33%. The recommended phase II dose (RP2D) is the dose with clinical efficacy without major toxicity.

- Any AE resulting in a dose delay of >7 consecutive days within the DLT period based on dose modifications in Table 9-6
- Non hematologic AE:
 - Hemorrhage requiring transfusion or procedural intervention, intracranial hemorrhage, intraocular hemorrhage of any grade
 - Grade 4 arterial hypertension
 - Any Grade ≥ 3 AE EXCEPT noted below
 - Grade ≥ 3 nausea, vomiting, constipation or diarrhea persisting for <48 hours
 - Grade ≥ 3 rash or skin hypersensitivity persisting for <7 days
 - <7 days of Grade ≥ 3 fatigue
 - <7 days of Grade ≥ 3 edema
 - <7 days of post infusion blood glucose >250 mg/dL despite optimal glucose management or <2 days of blood glucose >500 mg/dL despite optimal glucose management

- Grade 3 (or 4) isolated electrolyte abnormalities that resolve, with or without intervention, to Grade \leq 2 in less than 72 hours Hematologic AE
 - Any Grade 4 neutropenia lasting more than 7 consecutive days
 - Febrile neutropenia \geq Grade 3 (ANC $<1000/\text{mm}^3$ with a single temperature of $>38.3^\circ\text{C}$ or a sustained temperature of $\geq 38^\circ\text{C}$ for more than 1 hour

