9.6.3 Drug-drug Interactions

Guideline for Use of CYP Inhibiting/Inducing Drugs

Both ibrutinib and copanlisib are metabolized primarily by CYP3A4. Plasma concentrations of ibrutinib and copanlisib may be increased from concomitant use of strong or moderate CYP3A4 inhibitors. Consequently, strong or moderate CYP3A4 inhibitor and inducers should be avoided. Ibrutinib and its major metabolite (dihydrodiol) have been shown, in vitro, to be weak inhibitors and inducers of CYP450 isoenzymes. Note that with the data available, it is not possible to confirm whether such interactions will occur in patients. Therefore, investigators, at their discretion, may administer concomitant medications known to be metabolized by

CYP3A4/5, CYP2C8, CYP2C9 and CYP2C19. The use of moderate and strong CYP3A inducers and inhibitors is strictly prohibited during the DLT evaluation period.

During phase II, strong inhibitors of CYP3A such as ketoconazole, indinavir, nelfinavir, ritonavir, saquinavir, clarithromycin, telithromycin, itraconazole, and nefazodone, etc should be avoided. If strong CYP3A inhibitors cannot be avoided, consider holding ibrutinib and copanlisib while on CYP3A inhibitor if it will be used short-term. Re-initiate ibrutinib and copanlisib after 5 to 6 half-life washout period of the CYP3A inhibitor. If concurrent therapy with strong inhibitors cannot be avoided, reduce the copanlisib dose to 45 mg. If antifungal therapy is required, strong inhibitors of CYP3A4, including ketoconazole, itraconazole, posaconazole, and voriconazole should be avoided. Moderate inhibitors of CYP3A4, such as isavuconazonium sulfate, may be used. If used with a moderate CYP3A4 inhibitor, ibrutinib dosing should be reduced to 140 mg daily. No dose adjustment to copanlisib is needed. Avoid grapefruit and Seville oranges during ibrutinib treatment, as these contain moderate inhibitors of CYP3A (see Appendix 1).

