It is important that patients with pre-existing arterial hypertension adhere to their regular medication schedule and take their usual doses on the days of study drug infusion.

The management of acute blood pressure increases following copanlisib will need to be individualized for each patient, but experience in Phase I has suggested the benefit of dihydropyridine calcium channel blockers (i.e. amlodipine, felodipine). Topical nitrates should also be considered. Verapamil and diltiazem (non-dihydropyridine calcium channel blockers and moderate inhibitors of CYP3A4) should be used with caution due to a potential CYP3A4 interaction. In general, it is advisable for sites to be prepared, so that antihypertensive medication is readily available in case of need.

In the event of the occurrence of arterial hypertension \geq 150/90 mmHg during infusion of copanlisib at any cycle, antihypertensive treatment is suggested as indicated in Table 9-7. In the event of the occurrence of CTCAE Grade 3 arterial hypertension (\geq 160/100 mmHg) during infusion of copanlisib, the infusion should be interrupted and antihypertensive treatment as suggested above is administered. Infusion can be resumed when blood pressure has returned to $<150/90$ mmHg.

Guidelines for the monitoring and treatment of copanlisib induced hyperglycemia

Hyperglycemia is a common side effect of PI3K and also mTOR inhibitors. Hyperglycemia is often infusion-related and is dose-dependent. Transient increase of glucose levels have been observed in some patients. Regular monitoring of FPG to identify early hyperglycemia and prevent acute/sub-acute complications is important. Caution is warranted for patients with history of DM, or taking corticosteroids, or with other severe medical conditions (e.g. infections), or patients who show potential acute signs such as poly-nocturia, polydipsia, confusion, etc. Hyperglycemia management guidance includes patient education and dietetic measures/life-style changes as well as appropriate anti-diabetic medications as per investigator's decision and/or local guidelines.

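### Section 9.8 leaves verapamil and diltiazem usable with caution, while Section 9.6.3 bans moderate CYP3A4 inhibitors in the DLT period and cuts ibrutinib to 140 mg daily with them in phase II

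*Combined protocol and SAP*

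**What the plan says.** **Section 9.8**, under treatment of blood pressure increases associated with copanlisib, leaves management to the individual case but states a preference: "experience in Phase I has suggested the benefit of dihydropyridine calcium channel blockers (i.e. amlodipine, felodipine". Topical nitrates come next. It then turns to verapamil and diltiazem, identifies both as moderate CYP3A4 inhibitors, and says they "should be used with caution due to a potential CYP3A4 interaction". Nothing in that passage mentions cycle 1, the ibrutinib dose or Section 9.6.3.

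**Section 9.6.3** is the drug-interaction section. It gives the reason for concern: "Plasma concentrations of ibrutinib and copanlisib may be increased from concomitant use of strong or moderate CYP3A4 inhibitors". The general rule follows: "Consequently, strong or moderate CYP3A4 inhibitor and inducers should be avoided". For the DLT window the rule is absolute: "The use of moderate and strong CYP3A inducers and inhibitors is strictly prohibited during the DLT evaluation period". Section 9.2 sets that window as cycle 1, 28 days. In the paragraph on phase II, after an example about antifungal treatment, it says: "If used with a moderate CYP3A4 inhibitor, ibrutinib dosing should be reduced to 140 mg daily". It asks for no copanlisib change in that case.

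**Section 6.3** excludes a patient at entry in this situation: "Patient requires treatment with a strong or moderate cytochrome P450 (CYP) 3A4 inhibitors, and inducers, and the treatment cannot be discontinued or switched".

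**Section 9.1** gives the ibrutinib dose: "Patients will be instructed to take 420 mg or 560 mg depending on the treating cohort".

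**The concern.** Two sections give different instructions for the same two drugs. A clinician treating a blood pressure rise would naturally turn to Section 9.8, where the instruction is caution. Section 9.6.3 makes the same choice a prohibited one in cycle 1 of dose escalation, and in phase II one that requires a large ibrutinib reduction. Someone working from Section 9.8 alone could give a banned drug during the DLT window, or keep a phase II patient on full-dose ibrutinib when the protocol asks for 140 mg.

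What is at stake is the safety of the individual patient, since the protocol itself says that concentrations of both study drugs may rise. There is also a compliance consequence. Section 13.0 lists use of a prohibited medication among the reasons for stopping study treatment early, so on a literal reading a clinician who followed Section 9.8 in cycle 1 could trigger that rule.

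**Working it through.** No sample size, power or error rate depends on this point, so the check is a comparison of text plus one ratio.

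**1. Are the two drugs in the class that Section 9.6.3 regulates?** Yes. Section 9.8 itself calls them moderate CYP3A4 inhibitors, so no outside list is needed.

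**2. The two rules side by side**

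| Period | Section 9.8 | Section 9.6.3 |
|---|---|---|
| DLT evaluation period (cycle 1) | caution | strictly prohibited |
| Phase II | caution; no dose change mentioned | avoid; if used, ibrutinib 140 mg daily |
| Phase I after cycle 1 | caution | avoid; no dose given |

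In the first row the rules are incompatible as written. In the second, use with caution fits a conditional allowance, but the condition (the dose cut) is missing from Section 9.8. In the third, Section 9.6.3 has no dose rule, because the 140 mg instruction sits in the phase II paragraph.

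**3. Does the 140 mg rule reach these drugs?** It comes straight after text on antifungals, with one antifungal as the example. Its wording refers to a moderate CYP3A4 inhibitor in general, so it covers them.

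**4. Does another section reconcile the rules?** None does so expressly.
- Section 6.3 governs entry, not a drug started on study.
- The bulleted list in Section 9.6.2 names only strong CYP3A4/5 agents, and the moderate row of Table 9-5 names only fruit. That section says its list is a guide and not complete.
- Appendix 1 lists only strong agents.
- The hypertension rows of Table 9-7 call for blood-pressure-lowering treatment without naming drugs.
- Section 9.6.2 also bars anti-arrhythmic drugs other than beta blockers or digoxin. Section 9.8 presents these two as calcium channel blockers for blood pressure, so that bar does not clearly apply.

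**5. Size of the dose gap in phase II.** Inputs: 560 and 420 mg (Section 9.1), 280 mg (lowest step in Table 9-6), 140 mg (Section 9.6.3). Ratio = dose taken / 140.
- 560 / 140 = 4.0
- 420 / 140 = 3.0
- 280 / 140 = 2.0

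So even a patient already at the lowest toxicity reduction would be on twice the dose Section 9.6.3 asks for. The documents give no exposure effect for these drugs, so the ratios cannot be turned into exposure.

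**The case against.** The strongest reply is that this is only a missing cross-reference. Section 9.6.3 is the governing interaction section. Section 9.8 grants no exemption; it labels the drugs with the very class that Section 9.6.3 controls and gives the interaction as the reason for caution. It steers clinicians to dihydropyridines and nitrates. After the DLT window, caution is consistent with the phase II allowance. Most of this stands, and it is why the point is minor. It does not remove the conflict in cycle 1, where caution and strict prohibition cannot both apply, and it does not supply the dose instruction that Section 9.8 omits.

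A second reply concerns timing. Section 9.1 has ibrutinib taken in clinic just before the infusion, so when pressure rises during or after the infusion that day's dose is already in. Section 11.8 reports that six of eight previously untreated patients needed antihypertensives on the infusion day only. This also stands: the dose rule matters mainly when one of the drugs is given before the dose or continued on later days.

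A reader might infer more than the documents support:
- **That use would be common.** Section 11.8 puts post-infusion Grade 3 hypertension at about 42%. That is the rate of the event, not of use of these two drugs. The same section describes 8 + 7 = 15 patients given antihypertensive treatment and names neither drug.
- **That DLT attribution or the MTD would be distorted.** This needs a frequency of use and an exposure effect, and neither is given.
- **That patients would be over-exposed to ibrutinib 3- or 4-fold.** Those are dose ratios.
- **That Table 9-5 and Appendix 1 are a further failing here.** Section 9.8 already classifies both drugs.

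**Conclusion.** The point holds as a minor inconsistency in wording with a patient-safety side. Section 9.8 says caution where Section 9.6.3 says prohibited (cycle 1) or avoid, and otherwise 140 mg (phase II), and nothing in the protocol expressly reconciles them. In phase II the unadjusted ibrutinib dose would be 4 or 3 times the one called for, in a patient who is given one of the two drugs by a clinician relying on Section 9.8 alone. That should be infrequent, given the preferred alternatives and the entry exclusion, though the documents allow no estimate.

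The conclusion rests on two readings: that the 140 mg sentence applies to moderate inhibitors generally despite its antifungal lead-in, and that it applies in phase II only. The trial's design, sample size and endpoints are unaffected.

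**What to change.** Replace the verapamil and diltiazem sentence in Section 9.8 with text to this effect:

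> Verapamil and diltiazem (moderate CYP3A4 inhibitors) must not be used during the DLT evaluation period; use dihydropyridines or topical nitrates. In phase II they should be avoided or, if used, ibrutinib reduced to 140 mg daily while they are given, per Section 9.6.3.

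Two limits apply:
- If the sponsor wants the 140 mg rule in phase I after cycle 1 as well, it should be added to Section 9.6.3 as a new rule, because that section does not state it now.
- The two drugs should not be added to Table 9-5 unless marked as prohibited in the DLT period only. That table covers the whole study, so an unqualified entry would contradict the phase II allowance and could bring the Section 13.0 discontinuation rule into play.

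Appendix 1 and Section 9.7 need no change for this purpose. Section 9.7 already defines dose reductions by the steps in Table 9-6, and 140 mg is not one of them.

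The cost is a short wording amendment and a slightly narrower choice of antihypertensive in cycle 1, where Section 9.8 already names the alternatives.
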